# Vapotherm, Inc

## MODERATION Neo – Maintaining Optimal DEliveRy Using Automatic TItration of OxygeN Neonatal

Confidential

### Glossary of Definitions and Terms

**High Velocity Nasal Insufflation (HVNI):** a system consisting of heated and humidified gas mixtures of varying FiO2 delivered to a patient using a small-bore nasal cannula, at generally high flow rates imparted with increased velocity as compared to other standard large-bore cannulae. The flow rates of respiratory gas generally exceed a patient's normal spontaneous inspiratory flow demand. HVNI systems must maintain adequate heating and humidification of the delivered gas to protect the nasal tissues from dryness and provide patient comfort.

**Oxygen Assist Module (OAM):** this module utilizes a closed loop control algorithm, used in conjunction with the HVNI therapy provided by Vapotherm Precision Flow, that maintains patient oxygen saturation in an optimally controlled range (90-95%). In the Reynolds study this was labeled as the IntellO2 module.

**Pulse oxygen saturation (SpO2; %):** Arterial blood oxygen saturation as measured by pulse oximetry.

**Fraction of inspired oxygen (FiO2):** The fractional proportion (generally presented as a fraction but may be spoken of as percentage) of the delivered respiratory gas mixture that is oxygen.

**Case Report Form (CRF):** The form used to record pertinent patient data to address the study aim. CRFs do not contain patient names or medical record numbers; rather, they will be coded with a patient number and the key will be maintained by the site principal investigator at each center. The CRFs are the property of Vapotherm.

# Vapotherm, Inc

## MODERATION Neo – Maintaining Optimal DEliveRy Using Automatic TItration of OxygeN Neonatal

Confidential

### I. Background and Significance

The current study is designed to provide a technical validation for the Oxygen Assist Module (OAM; Vapotherm, Exeter, NH, USA) used in conjunction with the Vapotherm Precision Flow for titrating oxygen to neonates requiring non-invasive respiratory support. The Vapotherm OAM product integrates proven pulse oximetry and gas delivery technology with an innovative and proprietary algorithm that increases or decreases the FiO2 setting to assist the clinical staff in maintaining the patient in a target SpO2 range. The Vapotherm OAM product is a module for the Precision Flow device, which communicates with the Precision Flow through the serial interface connecting the two products: the device to the module. The Precision Flow is a Class II device and was FDA cleared (K072845) on July 17, 2008. The current Product Code under which the Precision Flow Hi-VNI is marketed is QAV. The initial Vapotherm OAM Gen0 design was used in a clinical trial in the UK (2016-2017, REC London-Chelsea 16/LO/1272, NCT02074774). The Vapotherm OAM, a module to the Precision Flow device, is designed to assist the caregiver in optimizing the patients' oxygen saturation levels, but is not life sustaining as it will not replace the standard of care provided to the infant; i.e., standard SpO2 alarms are in place and caregivers are instructed to make manual adjustments per standard care procedures.

Risk of both hyperoxia and hypoxia in preterm infants have been well described. The NeoProm Collaboration Meta-analysis confirmed that a lower SpO2 range was associated with a higher risk of death and necrotizing enterocolitis. Poets, et al., studied SpO2 values in 1019 infants born with a mean gestational age of 25.8 weeks, and birthweight of 855g who had hypoxic episodes of less than 80% SpO2 for longer than 1 minute had a significantly greater odds ratio (OR, 95%CI) for late-death or disability (3.4, 1.95-5.83), cognitive/language delay (2.88, 1.65-5.02), motor impairment (5.20, 2.48-10.92), and severe ROP (2.95, 1.47-5.90) versus episode length equal to or less than 50 seconds. As a result, many neonatal units target a higher range of SpO2, for example, 90%–95%. For staff, maintaining SpO2 targets presents a compliance challenge. Avoiding both hypoxia and hyperoxia is an important goal. While additional training improves compliance manual maintenance of the target range 90%–95% may only be achieved less than 50% of the time.

Based on prior studies, it is anticipated that the Vapotherm OAM will allow patients to spend more time in the target SpO2 range, with the potential for other benefits. In practice, the clinician sets the target SpO2, and the OAM uses a validated algorithm that combines analysis of real-time measurements and trending to choose the appropriate O2 delivery. The use of smart averaging and hysteresis algorithms protects the system from artifact causing too-rapid cycling of O2 delivery. The system alerts the health care provider if it is unable to maintain the target within the healthcare provider's set FiO2 limits or if maintaining the target requires a significant percentage change in the O2 percentage delivered. In the case of system detection of inadequate SpO2 signal, the module will alarm and revert to a clinician-set FiO2 setting. The Vapotherm OAM maintains trend data for both SpO2 readings and FiO2 settings that is captured every second.

# Vapotherm, Inc

## MODERATION Neo – Maintaining Optimal DEliveRy Using Automatic TItration of OxygeN Neonatal

Confidential

Closed loop control of inspired oxygen concentration has been in use since at least 1979 using indwelling PaO2 electrodes and since at least 1992 using pulse oximetry (SpO2). Cloure and Bancalari discuss the use of algorithms and trend data in closed loop FiO2 control systems for keeping SpO2 at “the target level or range set by the clinician” and summarize that “available data indicate the feasibility of automated closed loop control of FiO2 in this population [premature infants] and suggest potential benefits by achieving a better oxygenation control while limiting oxygen exposure.”

In a paper from 2009, Cloure and colleagues conducted a pilot clinical trial to evaluate a system for automated control of FiO2 in maintaining SpO2 within an intended range in preterm infants with erratic fluctuations in SpO2. The study involved sixteen infants with frequent hypoxia episodes and compared maintenance of SpO2 within the intended range during one 4-hour period of manual adjustment and one 4-hour period of automatic adjustment. This randomized study was conducted using the Avea ventilator with a built-in automated FiO2 adjustment function. The authors conclude that this system of automated FiO2 adjustment improved maintenance of SpO2 with reduced exposure to supplemental O2, but that studies of longer duration and with standard clinical conditions are warranted.

# Vapotherm, Inc

## MODERATION Neo – Maintaining Optimal DEliveRy Using Automatic TItration of OxygeN Neonatal

Confidential

automated system (81%;  $p < 0.01$ ) compared to routine management (54%) or intense manual control with adjustments every 2 to 5 min (69%). This original algorithm was used in a clinical study conducted at Cooper University Hospital in conjunction with Vapotherm's 2000i device (the predicate to the Precision Flow) interacting with a 'Smart Blender'. In the report of the Cooper study, Drs. Saslow and Pyon demonstrated in 14 subjects studied, using each patient as their own control, that patients spent 80% of the time within their predetermined saturation range versus 60% during the manual mode ( $p < 0.001$ ). Furthermore, the authors reported no adverse events associated with the use of the SmartBlender in either mode.

# Vapotherm, Inc

## MODERATION Neo – Maintaining Optimal DEliveRy Using Automatic TItration of OxygeN Neonatal

Confidential

## II. Objectives

The overall objective of this study is to demonstrate that the Vapotherm OAM, when coupled with the Precision Flow device, provides safe and efficacious automated control of fraction of inspired oxygen (FiO2) adjustments in spontaneously breathing infants with fluctuating arterial blood oxygen saturation levels in the routine clinical environment.

### Primary Safety Objective

To demonstrate that safety is not worse than standard practice. Specifically, to demonstrate that the Vapotherm OAM, used in conjunction with the Vapotherm Precision Flow Hi-VNI to treat infants with heated, humidified high velocity nasal insufflation (HVNI), is not inferior to standard practice for time that infants' arterial blood oxygen saturation exceed or drop below a target range, thus minimizing the proportion of time the subject is exposed to elevated or reduced levels of oxygen in the inspired gas.

### Primary Performance Objective

To demonstrate that percent time oxygen saturation is maintained in a target range is higher than standard practice. More specifically, to demonstrate that Vapotherm OAM used in conjunction with Vapotherm Precision Flow Hi-VNI is superior to standard practice for maintaining infants' arterial blood oxygen saturation in a target range, thus minimizing the proportion of time the subject is exposed to elevated or reduced levels of oxygen in the inspired gas.

### Secondary Performance Objective 1

To demonstrate that the percent time oxygen saturation is maintained in a target range is higher than standard practice for both weight categories (1000g-2500g, 2501g-3500g).

### Secondary Performance Objective 2

To demonstrate that the percent time SpO2 is maintained in a target range is higher than standard practice for subjects with both light and dark skin pigmentation.

### Additional Objectives

To quantify and compare OAM to standard practice performance with additional measures including:

- Proportion of Time, Number of Episodes, and Average Duration of Episodes in both high and low SpO2 ranges (with or without FiO2 at or above 21%)
  - SpO2 below target range
  - SpO2 below 80% for episodes  $\geq 60$ s
  - SpO2 below 80%
  - SpO2 above target range at FiO2>0.21 (not at air)
  - SpO2 below 70%
  - SpO2 in 80% to 86% range
  - SpO2 in target range at FiO2=0.21
  - SpO2 above 98% at FiO2>0.21 (not at air)

# Vapotherm, Inc

## MODERATION Neo – Maintaining Optimal DEliveRy Using Automatic TItration of OxygeN Neonatal

Confidential

- SpO2 below target range at FiO2=0.21
- Number of manual adjustments to FiO2 in manual mode compared to automated control (manual override).
- Proportion of Time at or below FiO2 ranges compared between study arms
  - FiO2 at 0.21 (air)
  - FiO2 below 0.25
- SpO2 fluctuations auto compared to manual control
  - Coefficient of variance for SpO2 for the study arm
  - Standard deviation of SpO2 for the study arm
- FiO2 fluctuations Auto compared to manual control
  - Coefficient of variance for FiO2 for the study arm
  - Standard deviation of FiO2 for the study arm
- Index of overshoot (an elevated SpO2 resulting from the FiO2 titration response to a low SpO2) and characterization of such excursions.
  - The proportion of time, number of episodes, and average duration per episode of Overshoot, defined as SpO2 > range following SpO2 < range for ≥10 seconds duration.
  - The proportion of time, number of episodes, and average duration per episode of Overshoot, defined as SpO2 > range for 70s following SpO2 < range.
- Number of Episodes of hypoxia (below range) within 60-180s after a return to FiO2=0.21 compared between arms.
- Number of Episodes of hypoxia (below range) within 60-180s after a return to FiO2=0.21 followed by hyperoxia (above range) within 60-180s after a return to FiO2=0.21 compared between arms.
- The mean FiO2 of the study arms
- Number of overall adjustments (or adjustments/hour) to FiO2 in manual mode compared to automated control.
- The care ratio (i.e., Nurse:Baby) will be recorded, patients will be separated to care ratio, and each care ratio group will be compared between study arms for the proportion of time, number of episodes, and average duration of episodes
  - SpO2 in target range
  - SpO2 below target range
  - SpO2 below 80% for episodes ≥60s
  - SpO2 below 80%
  - SpO2 below 70%
  - SpO2 in 80% to 86% range
  - SpO2 above target range at FiO2>0.21 (not at air)
  - SpO2 in target range at FiO2=0.21
  - SpO2 above 98% at FiO2>0.21
  - SpO2 below target range at FiO2=0.21
- Comparison between Day versus Evening/Overnight of the Proportion of Time, Number of Episodes, and Average Duration of Episodes in target, high, and low SpO2 ranges (with or without FiO2 at or above 21%) by study arm

# Vapotherm, Inc

## MODERATION Neo – Maintaining Optimal DEliveRy Using Automatic TItration of OxygeN Neonatal

Confidential

- SpO2 in target range
- SpO2 below target range
- SpO2 below 80% for episodes  $\geq 60$ s
- SpO2 below 80%
- SpO2 below 70%
- SpO2 in 80% to 86% range
- SpO2 above target range at FiO2>0.21 (not at air)
- SpO2 in target range at FiO2=0.21
- SpO2 above 98% at FiO2>0.21
- SpO2 below target range at FiO2=0.21
- CONSORT Diagram will be used to articulate the patient numbers
- For each arm of the study will aggregate the proportion of time for SpO2 for data bins from <80% to 100%, and displayed using a histogram.
- For each arm of the study will aggregate the proportion of time for FiO2 for data bins 0.21 to 1.0, and displayed using a histogram.
- Adverse events as reported on the CRFs (Summarized by seriousness and relatedness to therapy)
  - Specific Serious Adverse Event
    - Death
    - Necrotizing enterocolitis or focal intestinal perforation
    - Microbiologically-confirmed or clinically suspected late-onset invasive infection
    - Intracranial abnormality (hemorrhage or focal white matter damage) on cranial ultrasound scan or other imaging
    - Pulmonary hemorrhage
  - Specific Adverse Event Related to Therapy
    - Adverse Event from SpO2 Probe
    - Related to the oxygen delivery mode, either automated or manual

### III. Subject Selection

The **subjects** in this study are infants in neonatal intensive care units, born prematurely and requiring respiratory support via HVNI. The inclusion criteria are designed to identify infants who require supplemental oxygen and who therefore present an oxygen titration challenge by demonstration of spontaneous fluctuations in SpO2 requiring adjustment of FiO2.

As part of the interim analyses done by the data safety monitoring committee (defined below under Safety Monitoring), a review of data after every ten patients will confirm subject inclusion/exclusion criteria.

#### Inclusion Criteria

1. Infants delivered at a gestational age of less than or equal to 35 6/7 weeks (Preterm) being treated with high velocity nasal insufflation therapy for the management of respiratory distress syndrome

# Vapotherm, Inc

## MODERATION Neo – Maintaining Optimal DEliveRy Using Automatic TItration of OxygeN Neonatal

**Confidential**

2. Patients that clinically require SpO2 maintenance within the target range of 90-95%
3. A need for supplemental oxygen as demonstrated by a required FiO2 > 0.25 at enrollment
4. Requiring a flow rate of greater than 2 L•min such that the assumed inspired oxygen fraction matched delivered oxygen fraction (definition of HVNI).
5. A minimum of 6 manual FiO2 adjustments in the 24hr period prior to trial enrollment.
6. Willing/Able to complete informed consent.

### **Exclusion Criteria**

1. Current patient weight of <1000g or >3500g at time of study
2. Major congenital abnormalities
3. Hemodynamic instability, defined as being outside of a normotensive range based on an infant's individual characteristics by clinician
4. Persistent unresolved apnea defined as: requiring 6 stimulations or more per 6 hours
5. Seizures
6. Ongoing sepsis
7. Meningitis
8. Clinician's concern regarding stability of the infant

Infants who meet the inclusion criteria and none of the exclusion criteria will be considered. Informed consent will be obtained from the infant's Parent or guardian prior to enrollment in the study, following which appropriate profile and baseline data will be recorded on the subject's Case Report Form (CRF).

# Vapotherm, Inc

## MODERATION Neo – Maintaining Optimal DEliveRy Using Automatic TItration of OxygeN Neonatal

Confidential

### IV. Study Design

This study will be a prospective, multi-center, randomized, crossover trial of automated oxygen titration versus manual titration (conventional method). Patients enrolled will have their FiO2 managed by two mechanisms of titration (study arms) for two consecutive 24-hour periods in random order.

- Automated control (OAM), where the FiO2 is adjusted by the OAM system with clinical staff ability to override FiO2 when required, and instructed to do so – regardless of the mode
- Manual control (Manual), where FiO2 is only adjusted by the clinical staff

In both arms, the infants will be receiving high velocity nasal insufflation treatment using the Vapotherm Precision Flow Hi-VNI.

The study model does not change the nature of care that is provided by the clinical staff, and the clinical staff will be largely naive to the function of the OAM mode. Therefore, if the clinical staff see fit to change FiO2 during the Automated arm of the study they may override the module by changing the setting on the Precision Flow (without interacting with the OAM). Any manual override, and the justification for the override, will be noted on the subject's Case Report Form (CRF). SpO2 will continue to be monitored on the ICU patient monitors per standard of care.

In both study arms, data for FiO2, nasal cannula HVNI flowrate, gas temperature, SpO2 and pulse rate will be logged every 1 sec by the OAM, as well as being displayed / logged by the usual patient monitoring systems in each unit. Note that the OAM can log any manual adjustments during auto mode (overrides) as well as all data while in manual mode (Auto mode off). Offline computerized analysis will reduce the recorded data for both periods to assess time spent in the specified SpO2 range, time spent above and below the specified SpO2 range as well as other benchmark SpO2 values (see Data Collection and Statistical Analysis). Time spent below benchmark FiO2 values will be assessed (e.g., FiO2 at 21%, <25%). OAM data will be analyzed based on a modified intention-to-treat, whereby for any time the automated system is manually overridden in the 24-hour window, these outcomes data will be included into the analysis as well as the number of occurrences where manual manipulation is needed.

This study will be conducted at multiple sites, consisting of Academic Level III and IV Neonatal Intensive Care Units with proven record of experience in management of Preterm Infants requiring HVNI therapy delivered using the Precision Flow Hi-VNI technology. Each arm of the study will be assessed for 24 hours under routine clinical conditions. All staff members will be trained on the OAM operation and will have the ability to discontinue the study should the clinical condition of the patient require it.

### V. Statistical Methods and Data Analyses

Descriptive statistics will be used to summarize data including mean, standard deviation, median, range and interquartile range for continuous data, and counts and percent for categorical data. Hierarchical

# Vapotherm, Inc

## MODERATION Neo – Maintaining Optimal DEliveRy Using Automatic TItration of OxygeN Neonatal

Confidential

testing will be used to test the secondary objective(s). If both primary safety non-inferiority endpoints are passed and the primary performance endpoint is passed, we will test the secondary endpoint(s) for potential labeling claims. Analyses will be performed using SAS version 9.2 or higher, or comparable statistical software. Data from technically compromised data collection shall not be included in the analysis but will be described in detail if there are any instances.

*Technical Definition of Analyzed Target Range* – To be in line with common practice, for all data analyses the term ‘target range’ is defined as an  $\text{SpO}_2=90\%-95\%$  or an  $\text{SpO}_2=90\%-100\%$  if  $\text{FiO}_2=0.21$ . The analyzed targeted oximetric blood oxygen saturation range denoted as ‘target range’ in the safety performance, primary performance, secondary performance, and additional objectives/analyses is defined here, to include those babies who are not hypoxic ( $<90\% \text{ SpO}_2$ ) whilst on room air ( $\text{FiO}_2=0.21$ ). Thus, at  $\text{FiO}_2=0.21$ , an  $\text{SpO}_2=90\%-100\%$  is deemed within target range. These are not clinically deemed ‘out of target range’ when  $\text{FiO}_2=0.21$  (at air, Eupoxia), even when the  $\text{SpO}_2$  is greater than 95%. This definition of the analyzed target range does not change the clinical practice, as clinicians still target babies to a target range of  $\text{SpO}_2=90\%-95\%$  by adjusting  $\text{FiO}_2$  accordingly.

### **Analysis Cohorts:**

Full Analysis Set (FAS) – Subjects that are randomized and receive any period of time on at least one treatment will be included in the adverse event summary.

Modified Intent to Treat (mITT) – Subjects that are randomized and receive any period of time on both treatments will be included in the primary safety and performance endpoints.

Per Protocol (PP) – Subjects that are randomized, receive both the treatments as randomized (in the correct order) and without any major deviations (e.g., inclusion/exclusion violations, informed consent not obtained) will be included in the primary safety and performance endpoints as a supplemental analysis.

Challenge Population – Subjects in the PP with at least 6  $\text{FiO}_2$  adjustments in the manual arm will be identified as sufficiently labile subjects and will be included in supplemental analysis for safety and performance endpoints.

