#### Hypotheses:

Non-inferiority, proportion of time above range:

Ho:  $D \geq \delta$

Ha:  $D < \delta$ ,

where D = difference in proportion of time above range (OAM – standard practice) and  $\delta$  is the non-inferiority margin of 5.

Non-inferiority, proportion of time below range:

Ho:  $D \geq \delta$

Ha:  $D < \delta$ ,

where D = difference in proportion of time below range (OAM – standard practice) and  $\delta$  is the non-inferiority margin of 5.

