### **Primary Performance Objective**

Objective: To demonstrate that percent time oxygen saturation is maintained in a target range is higher than standard practice. More specifically, to demonstrate that Vapotherm OAM used in conjunction with Vapotherm Precision Flow Hi-VNI is superior to standard practice for maintaining infants' arterial blood oxygen saturation in a target range, thus minimizing the proportion of time the subject is exposed to elevated or reduced levels of oxygen in the inspired gas.

Endpoint: The proportion of time (expressed as a percentage) spent in the targeted arterial blood oxygen saturation range. The percentage will be measured by pulse oximetry (SpO2), to determine the ability of the OAM to effectively titrate FiO2 to the needs of the infant. This value will be assessed by abstracting and analyzing recorded data over two contiguous randomized 24-hour study periods; one period with automated control (OAM) and one 24-hour period with manual control.

Subjects to Analyze: Subjects in the mITT cohort will be the primary analysis. Additional supplemental analyses will repeat this analysis using the FAS, the PP and Challenge cohorts. This will be used to provide an Adverse Event(s) summary.

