# Vapotherm, Inc

## MODERATION Neo – Maintaining Optimal DEliveRy Using Automatic TItration of OxygeN Neonatal

Confidential

Analysis Method: The difference (OAM – standard practice) of the proportion of time in range will be tested using a paired t-test using a one-sided alpha of 0.025.

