## **Additional Analyses**

These exploratory analyses will use descriptive statistics to quantify values in each arm and the difference (OAM – standard practice). These analyses will use the mITT and PP populations except for adverse event summaries

To quantify and compare OAM automatic mode to standard manual practice performance with additional measures including:

- Proportion of Time, Number of Episodes, and Average Duration of Episodes in both high and low SpO2 ranges (with or without FiO2 at or above 21%)
  - SpO2 below target range
  - SpO2 below 80% for episodes  $\geq 60$ s
  - SpO2 below 80%
  - SpO2 above target range at FiO2>0.21 (not at air)
  - SpO2 below 70%
  - SpO2 in 80% to 86% range
  - SpO2 in target range at FiO2=0.21
  - SpO2 above 98% at FiO2>0.21 (not at air)
  - SpO2 below target range at FiO2=0.21
- Number of manual adjustments to FiO2 in manual mode compared to automated control (manual override).
- Proportion of Time at or below FiO2 ranges compared between study arms
  - FiO2 at 0.21 (air)
  - FiO2 below 0.25
- SpO2 fluctuations compared to manual control
  - Coefficient of variance for SpO2 for the study arm
  - Standard deviation of SpO2 for the study arm

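### The Challenge Population is selected on manual-arm FiO2 adjustments, a post-randomisation control-period measure, so its paired comparison is open to selection bias of unknown size and sign.

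*Combined protocol and SAP*

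**What the plan says.** Section V, Analysis Cohorts, starts from the per-protocol (PP) set and keeps infants with at least six FiO2 "adjustments in the manual arm will be identified as sufficiently labile subjects and will be included in supplemental analysis for safety and performance endpoints". The manual arm is one of the two randomised periods: under Section IV each infant is managed both ways "for two consecutive 24-hour periods in random order".

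The cohort's role is the same under the primary safety, primary performance and both secondary objectives. "Subjects in the mITT cohort will be the primary analysis", and then "Additional supplemental analyses will repeat this analysis using the FAS, the PP and Challenge cohorts". The analysis being repeated is a paired comparison. For time in range it "will be tested using a paired t-test using a one-sided alpha of 0.025". For time above and time below range it is tested against a limit that "is the non-inferiority margin of 5".

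Three other places matter:
- **Section III, inclusion criterion 5** requires at least six manual FiO2 "adjustments in the 24hr period prior to trial enrollment". The PP set excludes infants with eligibility violations, so every PP infant has already passed a threshold of six before randomisation.
- **Section VI** tells staff in the manual arm to titrate FiO2 in response to SpO2 alarms, and sets the monitor alarms at 90% and 95%, the limits of the target range.
- **Section V, Additional Analyses** lists the number of manual-mode adjustments as a measure to be compared between modes.

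**The concern.** Because criterion 5 already demands six adjustments, the Challenge rule can only remove infants whose manual study period turned out quieter than their pre-enrolment day. Section VI ties the count to the comparator outcome: SpO2 outside 90% to 95% sets off alarms, and alarms prompt adjustments. An infant whose manual day was worse than usual by chance is more likely to be kept, and one whose manual day was better than usual is more likely to be dropped. Nothing comparable is asked of the automated day, which sits on average at the infant's usual level. The mean paired difference in the subset can then move away from zero even if the two modes are equal.

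What is at stake is the supplemental result presented for labile infants, across time in, above and below range. A reader would take it as an estimate of how OAM performs in the hardest-to-titrate infants. As defined, the subset cannot separate that from a selection effect.

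**Working it through.** **Plan's own figures.** The documents give no figure for this cohort: no expected size, no count distribution, no correlation with SpO2 outcomes. The standard deviation (SD) used below is the plan's. With SD 11, difference 6, two-sided alpha 0.05 and 90% power, an exact paired t-test needs n = 38. The nonparametric adjustment gives 38 × π/3 = 39.8, which reproduces the stated 40.

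**Inputs from the documents** (Section V, Sample Size Calculations): SD of the paired difference 10.8 for time in range, 10.8 for time below and 16.2 for time above; expected difference in time in range 28.4; non-inferiority margin 5.

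**Assumed inputs:** q, the share of PP infants reaching six; ρ, the correlation of the manual-arm count with the paired difference, signed so that positive ρ favours OAM.

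**Step 1, closed form.** If selection acts on an approximately normal score, with φ the normal density at the cut z_q,

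bias = ρ × SD × φ(z_q) / q.

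The factor φ(z_q)/q is 0.195 at q = 0.90 and 0.798 at q = 0.50. For example, ρ = 0.3 and q = 0.90 for time in range gives 0.3 × 10.8 × 0.195 = 0.63 points.

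| q | Time in or below range (SD 10.8), ρ = 0.1 to 0.5 | Time above range (SD 16.2), ρ = 0.1 to 0.5 |
|---|---|---|
| 0.95 | 0.1 to 0.6 | 0.2 to 0.9 |
| 0.90 | 0.2 to 1.1 | 0.3 to 1.6 |
| 0.80 | 0.4 to 1.9 | 0.6 to 2.8 |
| 0.50 | 0.9 to 4.3 | 1.3 to 6.5 |

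The table shows the size of the shift in OAM's favour. In this grid only q = 0.50 with ρ = 0.5 exceeds the margin of 5.

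**Step 2, effect on the test.** With 40 PP infants, a true difference of zero and 20,000 runs, the nominal one-sided 0.025 test rejects as follows:
- q = 0.90: 0.041 (ρ = 0.2) to 0.085 (ρ = 0.5)
- q = 0.80: 0.059 to 0.171
- q = 0.50: 0.098 to 0.451
- ρ = −0.3, q = 0.90: 0.011, with bias −0.6 points
- ρ = 0: 0.023 to 0.027, no bias

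**Step 3, a count model in place of ρ and q.** Assume time out of range is an infant mean (50, SD 10) plus independent period noise (SD 7.6, so the paired SD is 7.6 × √2 = 10.7). Counts are Poisson or overdispersed and rise with that period's time out of range (log-slope 0.2 to 0.4 per 10 points). Eligibility is six or more before enrolment, and Challenge is six or more in the manual period. The modes are equal.
- Mean count 8 to 12 per 24 h: bias about 0.3 to 1.5 points in favour of OAM.
- Mean count 5: bias up to about 2.6 points. Only about 40% of simulated infants then meet criterion 5, so this setting sits poorly with the enrolled population.
- All eligible infants, without the Challenge rule: bias 0.

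**Step 4, against the expected effect.** 1.5 / 28.4 = 5% and 2.6 / 28.4 = 9%.

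**Side check.** The threshold is a raw count, and Section VII treats manual arms of 12 to 18 h as minor violations only. With an assumed Poisson mean of 10 per 24 h, 93% reach six in a full arm, 76% in 18 h and 38% in 12 h, so selection depends partly on recording time.

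**The case against.** A reader might infer that the cohort is biased by construction in favour of OAM. The documents do not support that.
- Every selected infant contributes both periods, so stable differences between infants cancel. Bias needs the count to correlate with the period-specific part of the paired difference, and the documents report no such correlation.
- The direction is not fixed. Many adjustments may mark an unstable day, which inflates the OAM benefit, or attentive staff with good manual control, which shrinks it.
- All infants passed a threshold of six before enrolment, so most may pass again. The bias would then be small.

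A reader might also infer that the trial's conclusions or labelling claims are at risk. They are not: mITT is primary, secondary testing depends on the primary endpoints, and no decision is attached to the Challenge result.

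The cohort also has a sensible descriptive aim: to show performance when the study period really did pose a titration challenge. Lability before enrolment need not persist, so a baseline rule answers a somewhat different question.

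All of this stands, and it limits the size and consequence of the point. It does not remove it. Section VI supplies a plausible mechanism linking the count to the comparator outcome, and the plan repeats formal tests in the subset without any caveat.

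**Conclusion.** The point holds in a limited form. The Challenge comparison is conditioned on a post-randomisation measure seen only under control, and can be distorted by regression to the mean. The size is about 0.3 to 1.5 points of time in range for mean counts of 8 to 12 per 24 hours, and about 2.6 only near a mean of 5. These figures rest on assumed count means, slopes and noise that the documents do not give, and the sign could reverse. The primary inference and its alpha are untouched, and the expected time-in-range conclusion would survive. What the subset cannot provide, as defined, is a clean estimate or a valid 0.025-level test in labile infants, including the repeated non-inferiority tests. The change is worth making because it is cheap, not because the trial depends on it.

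**What to change.** Base the supplemental lability analysis on pre-randomisation data. Model the paired difference (time in, above and below range) on the number of manual adjustments in the 24 hours before enrolment, the count that criterion 5 already requires. Alternatively, define a subset by a baseline cut above six, fixed in advance. A baseline cut of six would return the whole PP set, and a cut at the sample median would be known only after enrolment. Since order is randomised after this count is taken, conditioning on it cannot favour either mode; the simulated type I error with no correlation is 0.023 to 0.027.

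If the manual-arm subset of six or more is kept, report it as descriptive only, without non-inferiority or superiority tests, and state how many PP infants it excludes.

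Cost: revised SAP wording and at most one CRF field. The baseline list in Section VII does not name the count, although the CRF itself is not in the public document and may already hold it. The downside is a less direct description of infants who were labile during the study period itself.
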